## Introduction

### Background and Rationale

Heart failure (HF) affects more than 8 million Americans and is increasing at a rate of 46%, with an increase in costs of up to \$70 billion annually [1]. Severe symptoms of HF persist despite medical, surgical, or HF device therapy [2]. HF is a debilitating and life-limiting disease that requires extensive home family caregiving assistance and difficult decisions regarding treatment options for patients who are experiencing progressive decline [3, 4]. Studies verify family caregivers contributions to HF home care. Worsening HF has numerous negative impacts on family caregiver health outcomes, resulting in caregiving burden [3, 5]. In turn, the caregiving burden can have a negative impact on caregiver's physical and mental health status [5]. Family caregivers managing patient HF reported unmet needs, [6] lack of communication with health care professionals, [7] and little if any preparedness for home end-of-life and palliative care (EOLPC) [8].

Patients and their families are unprepared for the challenges of this deteriorating condition and for home caregiving burdens. Most have fears of suffering a painful death [9, 10]. Our nurse-led family home EOLPC intervention (FamPALcare) addresses these challenges [11]. Palliative care includes supportive and comfort care to relieve patient suffering and pain/discomfort [12]. HF palliative care also includes treatments specific for the distressing, commonly repeating physical and psychological symptoms of HF (e.g., breathlessness, fatigue, edema, and depression/anxiety). HF palliative care includes discussions for determining the HF care options according to the families' end-of-life (EOL) care preferences [13].

Further, patients with HF who live in rural areas have higher mortality rates than those who live in urban areas [14]. Specifically, in West Virginia (WV), where HF death rates are the highest in the country, residents have limited access to healthcare and experience social service inequities [15, 16]. The rural mountainous terrain and distance from HF specialists and local healthcare services increase the family caregivers' need for more useful home care information [17]. Home palliative care interventions can assist families in managing advancing HF symptoms and end-of-life (EOL) care needs at home [18].

Considering the burden of families managing HF, the increasing prevalence of palliative care needs [19], and the lack of palliative care providers [20], home HF palliative care is understudied with little guidance or information to support caregivers [21, 22]. Thus, family caregivers need preparation for complex home care and palliative care specific to HF with considerations for families in rural settings with limited services [23]. Effective palliative care should incorporate patient cultural values and preferences about their disease state and medical treatment [24]. Preparing caregivers for providing HF home care can reduce patient and caregiver anxiety and help them discuss their end-of-life preferences [25].

### Purposes

The purpose of this study is to test whether a home palliative care intervention (FamPALcare) would improve family caregiver and patient HF-related health status and their depression/anxiety scores at 3- and 6-month endpoints. Another purpose is to verify the feasibility, fidelity, helpfulness and costs of FamPALcare remote telephone intervention delivery.

---

## Objectives

The following specific aims, directional hypotheses, and research questions are:

**Primary Aim:** To test whether the FamPALcare nursing care intervention could reduce the burden of family caregivers by preventing caregiver depression/anxiety and improve patient HF-related health status and depression/anxiety. The hypotheses and research questions are as follows:

*Aim 1.1* Compared to those in the control group at 3 and 6 months, the caregivers who receive FamPALcare will have significant improvements in home caregiving burden and depression/anxiety scores.

*Aim 1.2* Compared to those in the control group at 3 and 6 months, patients in the FamPALcare group will experience greater improvement in HF-related health and depression/anxiety scores.

**Secondary Aim:** To assess the feasibility and fidelity of the FamPALcare intervention.

*Aim 2.1.* What are the participant recruitment, enrollment, and retention outcomes?

*Aim 2.2.* How helpful the FamPALcare as rated by participants on the anonymous 11-item Helpfulness Questionnaire?

*Aim 2.3.* What is the FamPALcare implementation cost using traditional tabulated cost-minimization analysis?

## Study Design

### *Overall Design*

This study uses a randomized controlled trial (RCT) design to test the FamPALcare intervention. The RCT design is consistent with the National Template for Intervention Description and Replication (TIDieR) checklist and guide [30].

### *Study Population*

Adult ( $\geq 18$  years) end-stage HF patients (NYHA III and IV and Stages C and D) and their family caregivers who are involved in daily home care will be recruited.

### *Inclusion and Exclusion Criteria*

Inclusion criteria are dyads of family caregivers and patients with advanced systolic and diastolic HF [2, 10]. The cardiology consultants specify inclusion of patients with both systolic and diastolic dysfunction as both require similar HF home care management regimens and have similar advanced EOL symptoms, which FamPALcare can address. All participants must be alert and oriented, provide written consent, and be able to read and write in English. Family caregivers are those designated by the HF patient as non-paid primary persons who assist with HF home care, thus not requiring the dyad to be spouses. Exclusion criteria are patients who have received or are on a waiting list for a heart transplant and those with a terminal illness or dementia, such as Alzheimer's disease. Also excluded are caregivers with a disability that precludes their use of FamPALcare intervention materials such as those suffering with dementia or Alzheimer's disease.

### *Randomization and Blinding*

This RCT uses random assignment to group with stratification of the patient sex (male vs female) to equalize distribution. SPSS version 29 is used to generate random numbers within each group. Each family dyad is randomly assigned to either the control or intervention group in a 1:1 fashion [11]. The researchers are blinded to the group assignments until informed consent is obtained. The Institutional Review Board of the University Health Sciences Center (WVU IRB 1709754988) approved the study protocol.

## Study Procedure

Both patients and caregivers will provide consent and will be randomly assigned to a study group as a dyad. Permission to review patients' hospitalization medical records will be obtained per IRB, as in the previous studies. Recruitment is from sites affiliated with WVU Hospital (WVUH) including local health centers or clinics, churches, physician offices, and community centers throughout Appalachia. Personnel

---

who already have clinic responsibilities and access to patient records, consistent with HIPAA requirements, will perform subject eligibility screening and the initial recruitment contact.

## **Study Intervention**

### ***Standard care group***

In this study, all patients and their family caregivers continue the standard health care prescribed by their healthcare providers. Patient standard HF care includes routine educational materials given to them at the outpatient clinics or upon hospital discharge planning.

### ***Family home palliative care (FamPALcare) intervention group***

Participants in the intervention group receive standard care and the FamPALcare intervention. FamPALcare aims to provide family caregivers with practical skills for managing patient symptoms and deterioration of their HF status, addressing palliative care needs and home caregiving burden. The FamPALcare clinician nurse will coach patients and their family caregivers on HF palliative symptom management and guide advanced directives discussions.

Intervention participants (Group 1) will receive five coaching sessions with telephone follow-up to reinforce intervention home care. The nurse interventionists will engage each FamPALcare dyad in weekly FamPALcare coaching sessions scheduled at times and locations (home, church, or private room in outpatient clinic) convenient to the patient/family. Each coaching session lasts about 60-120 minutes. **Sessions include:** **Week 1:** developing rapport, identifying HF home care needs, assessing caregiver involvement in home care, and motivating multiple family caregivers to coordinate home care and be involved in their home HF EOLPC plan. **Week 2:** supporting home care skills to manage advanced HF and worsening HF symptoms and discussing the families' EOL beliefs. **Week 3:** discussing sensitive HF EOLPC options and preparing advance directives. **Week 4:** coaching on managing caregiver burden and seeking professional help/community support. **Week 5:** reinforcing skills specific to advanced HF home care and practicing early symptom reporting to clinicians. The nurse will coach the patient and family in making decisions about EOLPC options based on their preferences and on having the advance directives forms signed and taken to their next doctor appointment. Telephone contact will be conducted at 1-month post-intervention to allow sufficient time for family members to discuss their EOLPC decisions and generate questions.

The FamPALcare intervention manual includes pictures of an advanced scientific-based HF disease progression trajectory graph. The graph is used to explain the typical expected HF decline and how to handle common bothersome HF symptoms (e.g., breathlessness, anxiety/depression, edema, fatigue). In addition, examples of advanced directives forms, Physician Orders for Scope of Treatment (POST) (e.g., do not resuscitate) forms, and local emergency contacts are provided [36]. The FamPALcare clinician will recommend that forms be taken to the patient's next healthcare provider's appointment to sign and document in their medical records. Participants keep the FamPALcare manual with these informative and illustrated guidelines as well as contact lists for any available resources. The FamPALcare clinician follows the HF educational manual, which includes coaching strategies for discussing the sensitive topic of end-of-life care [37] and includes specific information regarding standard palliative and end-of-life care options. The FamPALcare clinician uses an open-ended coaching conversation approach to facilitate patient wishes and preferences regarding end-of-life care.

### ***Compliance Monitoring***

The FamPALcare manual provides families with step-by-step guides and visual illustrations for managing HF declines. These FamPALcare materials are designed to support home caregivers and patients with low literacy levels and to overcome barriers to providing adequate HF home care [19]. To ensure that participants fully comprehend the information discussed during each FamPALcare session, the clinician will utilize the effective "teach-back" technique [27]. By asking participants to describe what they had been taught, the nurse ensures that the information has been conveyed accurately and understood completely.

The nurse also identifies any topics that require further reinforcement for future retraining in the follow-

---

up telephone calls. Furthermore, after three months, a follow-up phone call is made to provide additional support and encourage the continued practice of FamPALcare. A second trained clinician who observes the FamPALcare clinician at randomly selected FamPALcare sessions will confirm the fidelity of the intervention. This clinician documents the accuracy and consistency of the FamPALcare intervention implementation according to the manual [38]. Our research quality assurance measures include quarterly communication and intervention retraining and protocols for data collection monitoring [29].

## **Safety and Adverse Events**

### ***Safety Assessments***

Adverse event is any unfavorable and unintended sign, symptom or disease temporally associated with the use of a medical treatment or procedure, regardless of whether it is considered related to the medical treatment or procedure. The Safety Monitoring Committee (SMC) will include two experts who are independent of the study protocol. The SMC members are (1) a palliative care nurse and (2) a Biostatistician who has extensive experience in randomized clinical trial (RCT) studies. The SMC will review each potential adverse event (AE) upon its occurrence (real-time) and bi-annually thereafter. The PI and Co-I will conduct bi-annual meetings with SMC to review the AEs tabulation of all AEs accumulating across the study to identify any possible repeating patterns. Also, the SMC members review any records of adverse events (AEs) and anecdotal notes related to our IRB approved procedures for Depression Prevention and Referrals on a monthly basis. The SMC will provide direction to address any ethical issues that may arise related to palliative care or end-of-life discussions, study safety, and research risks.

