### ***Adverse Event Reporting***

The SMC will ensure that the PI provides timely reports to IRB and NINR if unanticipated problems or unexpected serious AEs related to the study protocol arise. The interim data analysis will be reported to SMC at the bi-annual meetings. If warranted, the SMC may provide advice and feedback on data analysis to the study statistician. The SMC will make recommendations as appropriate as to whether the trial should continue as originally designed, be changed, suspended or terminated, based on the observed beneficial or adverse effects of any of the treatments under study. These recommendations and actions taken will be reported to the IRB and NINR.

All research staff will notify the PI within 24 hours if any potential study safety risks arise. The PI notifies the IRB within 24 hours and notifies NINR within 7 days of the investigator becoming aware of the event. The biostatistician reviews data quality management procedures and all statistical analyses. The Co-I and team members work with the PI to carefully interpret and disseminate the study results.

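### Adverse event detection is open to surveillance bias: about 8 or 9 scheduled study contacts after baseline in the intervention group, at least two in the control group, and no common adverse event inquiry

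*Combined protocol and SAP*

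**What the plan says.** **Safety review.** Under Safety Assessments, the SMC looks at each potential AE as it occurs. At bi-annual meetings it joins the investigators to "review the AEs tabulation of all AEs accumulating across the study to identify any possible repeating patterns". Each month it also looks at AE records and at anecdotal notes linked to a depression prevention and referral procedure. Under Adverse Event Reporting, it may recommend that the trial continue, change, pause or end, "based on the observed beneficial or adverse effects of any of the treatments under study". Safety signals reach the principal investigator through research staff, who must pass them on within a day.

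**Contact with the intervention group.** The intervention section states: "Intervention participants (Group 1) will receive five coaching sessions with telephone follow-up to reinforce intervention home care". It adds: "Each coaching session lasts about 60-120 minutes". It also states: "Telephone contact will be conducted at 1-month post-intervention". Compliance Monitoring adds that "after three months, a follow-up phone call is made to provide additional support and encourage the continued practice of FamPALcare".

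**Contact with the control group.** Under Standard care group, "all patients and their family caregivers continue the standard health care prescribed by their healthcare providers". No study contact is described there.

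**Contact common to both.** Data Collection Methods has data collected from everyone at baseline and at 3 and 6 months, by collectors blinded to group. The same section mentions separate research nurses for the control group, without a schedule, and a home care checklist at 3, 6 and 12 months, without saying which group completes it.

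**What is not stated.** The plan defines an AE broadly, whether or not it is related to treatment. It does not say who asks about AEs, when, with what form, or that the two groups are asked alike.

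**The concern.** When events come to light through staff contact, and one group has several times as much of it, the two groups can have the same true event rate and different recorded counts. The content of the contact may widen the gap. The coaching covers worsening symptoms, end-of-life beliefs and caregiver burden, and its last session rehearses prompt reporting of symptoms to clinicians. Controls have no described counterpart. Timing differs too: a control event may surface only at month 3 or 6, so real-time review may not work equally in the two groups.

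The stake is the SMC's judgement. An excess in the intervention group could be read as harm from FamPALcare when it reflects closer observation, or a real harm could be put down to closer observation. With 18 dyads per group, a few extra recorded events could look like a pattern. If the source of detection is not recorded, the two explanations cannot be told apart afterwards.

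**Working it through.** The plan states neither a total number of contacts nor an expected AE rate, so it has no figure of its own to reproduce. The check has three steps.

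**1. Scheduled contacts after baseline, to 6 months**

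| Contact | Section | Intervention | Control |
|---|---|---|---|
| Coaching sessions, weeks 1 to 5 | Intervention group | 5 | 0 |
| Call 1 month after the intervention | Intervention group | 1 | 0 |
| Support call after three months | Compliance Monitoring | 1 | 0 |
| Data collection at 3 and 6 months | Data Collection Methods | 2 | 2 |
| Total | | 9 | 2 |

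- The ratio is 9/2 = 4.5. With 18 dyads per group that is 18 × 9 = 162 against 18 × 2 = 36 dyad contacts.
- If the support call coincides with the 3-month data collection, the count is 8 against 2.
- A 12-month checklist contact would make it 10 against 2 if only the intervention group completes it, or 10 against 3 if both do.
- Two is the minimum described for controls, because the control-group nurses have no stated schedule.
- The coaching sessions alone amount to 5 × 60 = 300 to 5 × 120 = 600 minutes, that is 5 to 10 hours per dyad.

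**2. What this could do to recorded counts when true rates are equal (all rates assumed)**

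*Persistent event.* Let q be the chance that it is picked up at any one contact and k the number of contacts. Detection = 1 − (1 − q)^k.

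| q (assumed) | Intervention, k = 9 | Control, k = 2 | Ratio |
|---|---|---|---|
| 0.05 | 37% | 10% | 3.8 |
| 0.10 | 61% | 19% | 3.2 |
| 0.20 | 87% | 36% | 2.4 |
| 0.50 | 99.8% | 75% | 1.3 |

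For example, q = 0.10 gives 1 − 0.9^9 = 0.613 and 1 − 0.9^2 = 0.190, a ratio of 3.2. With k = 8, the top row becomes 1 − 0.95^8 = 0.337 against 0.0975, a ratio of 3.5.

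*One-off event.* Events fall evenly over 26 weeks and are reported at the next contact with probability 0.5^(wait/h), where h is an assumed recall half-life in weeks. Contacts are placed at weeks 1 to 5, 9, 13 and 26 for the intervention group (support call and 3-month data collection in the same week) and at weeks 13 and 26 for controls.

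| h (assumed) | Intervention | Control | Ratio |
|---|---|---|---|
| 2 weeks | 44% | 22% | 2.0 |
| 4 weeks | 60% | 40% | 1.5 |
| 8 weeks | 74% | 60% | 1.24 |
| 13 weeks | 83% | 72% | 1.14 |
| 26 weeks | 90% | 85% | 1.07 |

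Across both models the ratio runs from 1.07 to 3.8, and the excess is always in the intervention group.

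**3. Effect of counting only common contacts**

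With k = 2 in both groups, detection is 1 − (1 − q)^2 in each, so the ratio is 1.0 for any q that is equal in the two groups.

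**The case against.** The strongest reply is that the documents contain no comparison to distort. Safety Assessments describes case-by-case review and then a tabulation across the study. No table by group is stated, and the Statistical Analysis Plan has no AE analysis. This stands in part: the comparison has to be inferred from the SMC's remit, which refers to effects of any of the treatments. That remit is hard to exercise without looking at the groups side by side, but it does not show that a distorted comparison will be made.

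Second, contacts are not ascertainments. The plan does not say that AEs are asked about at any of them, and control contacts may exceed two. Permission to review hospitalization records (Study Procedure) could supply an equal source for admissions, although the plan does not say that it is used for AEs, and it would miss caregiver distress and symptoms that do not lead to admission. All this bears on the size of the bias. It does not supply a common inquiry.

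Third, a reader might infer that depression referrals share the imbalance, and that part of any benefit on depression/anxiety would then come from referral and not from coaching. The documents do not support this. The referral procedure is not reproduced, so its trigger is unknown. It could be the scores collected from everyone, which would be symmetric. The week 4 session also coaches families to turn to professionals and community services, so help-seeking is partly an intended effect of FamPALcare.

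Fourth, restricting the comparison to events elicited at 3 and 6 months would set aside distress that surfaces in the end-of-life sessions and would lose participants who die before interview; the sample size section expects 20% attrition from heart failure deaths. This is correct, and it is why the all-source count has to stay beside the common one.

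**Conclusion.** The concern holds as a susceptibility to bias. Following the plan as written leaves AE detection open to differential surveillance, with 8 or 9 scheduled contacts against a described minimum of two and nothing that makes the inquiry alike. It cannot be said that the SMC's view is distorted, or that equal event rates will look like harm: no by-group table is stated and the true detection rates are unknown.

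The range of about 1.1 to nearly 4 rests wholly on assumed pick-up and recall rates. It also assumes equal true event rates, the same pick-up chance per contact in both groups, and only two control contacts. If recall at 3 and 6 months is nearly complete, or hospital records are used equally in both groups, the ratio moves towards 1. Under these assumptions the direction does not change. The referral question supports better recording and nothing more.

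**What to change.** In Safety Assessments and Data Collection Methods:

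1. Have the blinded data collectors put one identical structured AE question set to patients and caregivers in both groups at 3 and 6 months.
2. Record the source of detection for every AE: common data collection, coaching session or support call, or other.
3. Show the SMC all AEs by group and by source. Use the common-time-point count as the like-for-like comparison, and place the all-source count, including deaths, beside it.
4. Leave all existing reporting and review of individual events unchanged.
5. Record each depression referral with its date, group and triggering contact, and present the counts by group as description only.

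The cost is one short form at interviews that already take place, a few minutes each, and extra columns in the SMC table. The limits are recall over about 3 months and no interview from participants who die or drop out, which the all-source table partly covers.

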### ***Adverse Event Reporting***

The SMC will ensure that the PI provides timely reports to IRB and NINR if unanticipated problems or unexpected serious AEs related to the study protocol arise. The interim data analysis will be reported to SMC at the bi-annual meetings. If warranted, the SMC may provide advice and feedback on data analysis to the study statistician. The SMC will make recommendations as appropriate as to whether the trial should continue as originally designed, be changed, suspended or terminated, based on the observed beneficial or adverse effects of any of the treatments under study. These recommendations and actions taken will be reported to the IRB and NINR.

All research staff will notify the PI within 24 hours if any potential study safety risks arise. The PI notifies the IRB within 24 hours and notifies NINR within 7 days of the investigator becoming aware of the event. The biostatistician reviews data quality management procedures and all statistical analyses. The Co-I and team members work with the PI to carefully interpret and disseminate the study results.

